Emotion regulation training for adolescents with ADHD

Study Protocol (including analysis plan)

This is a brief protocol and proposed plan for data analyses corresponding to the pre-registered research aim: *To evaluate feasibility and potential effectiveness of a psychological intervention (SKILLS-ER) designed to strengthen adaptive regulation skills for adolescents with ADHD.* Due to unforeseen conditions related to data or other unexpected circumstances, this plan may have to be revised.

Intervention

The intervention (SKILLS-ER) has been developed by the authors, and aims to increase a participant's emotion regulation capacity by targeting different stages of the emotion regulation process proposed by the extended process model of emotion, i.e., identification, selection, implementation and monitoring (Sheppes et al., 2015). SKILLS-ER will comprise of eight sessions and include identification and differentiation of emotions, tolerance/acceptance of emotions, education of different regulatory skills, as well as on how to select, implement and monitor strategies. Sessions will take place at the Uppsala child- and adolescent psychiatry unit and consist of activating and experiential exercises administered by a clinical psychologist. Participants will gain access to internet-delivered material, such as homework assignments in-between sessions. SKILLS-ER will be delivered individually to the participants, where their parents will be involved in some sessions.

Participants

Adolescents (n=9; 13-18 years of age) with ADHD and emotion dysregulation will participate in SKILLS-ER in order to evaluate feasibility, potential effectiveness and to detect mechanisms that could strengthen adaptive regulation skills. The participants will be recruited from Uppsala child and adolescent psychiatric outpatient unit. Inclusion criteria is an ADHD diagnosis and self- and/or parent-rated emotion regulation difficulties, as indicated by the Emotion Questionnaire, on which the adolescent and parent rate either "strongly disagree" or "disagree" on the specific item: "when I (he/she) am (is) angry/sad/afraid/happy I (he/she) can change my (his/her) mood" (note: this item encompasses four separate questions related to being i) angry, ii) sad, iii) afraid or iv) happy). Further, emotion regulation difficulties should be identified as a problem for the adolescent. Exclusion criteria includes intellectual disability, autism, psychosis, bipolar disorder, severe depression, non-stabilized medication for ADHD at intake (if on medication for ADHD), and other ongoing psychological treatment.

Study design

A single-case multiple baseline design will be used, where the participants will be randomized to pre-intervention concurrent baselines at different lengths (5, 6 and 7 weeks).

Primary outcome measures: Rated emotion regulation

The participants and their parents will rate emotion regulation weekly using the Difficulties in Emotion Regulation Scale Short Form (DERS-SF; Kaufman et al., 2016). In addition, the parents will rate two daily measures of individually defined target behaviors associated with emotion regulation of their child (e.g., number of tantrums), collected during all phases (baseline [5-7 weeks], intervention [8 weeks] and post-intervention [2 weeks]). We will analyze the data with a combination of visual and quantitative analyses. For the visual analyses, we will follow the steps outlined by Kratochwill and colleagues (2013), investigating level, trend, variability, immediacy of effect, overlap and consistency of data patterns. To complement the visual analyses, we intend to use Tau-U as an effect size measure. We will follow the recommendations by Fingerhut and colleagues (2021) to decide which specific index of Tau-U is most appropriate in relation to the data as indicated by visual inspection.

Hypotheses

We hypothesize that emotion dysregulation (operationalized as the total summed score of DERS-SF) will decrease and that the individually defined target behaviors will change in frequency (with a decrease of emotion dysregulation or increase in emotion regulatory behaviors) during the intervention, comparing baseline with the intervention phase, and that any effect will remain up to two weeks after the intervention. In addition, we expect to see changes in the DERS-SF subscale scores during the intervention in a manner that corresponds to specific sessions dealing with content relevant to certain subscales. We hypothesize that ratings of the emotional awareness and clarity subscales will change first in the treatment, followed by the subscales nonacceptance, engaging in goal-directed behavior and emotion regulation strategies. Further, we hypothesize that time to change will be related to start of intervention, not start of baseline. An exploratory hypothesis will be adopted for the impulse subscale since it may correlate more with ADHD core symptomatology than other subscales and may not be as sensitive to the effects of the emotion regulation training.

Secondary outcome measures: Rated emotion regulation, functional impairment, client satisfaction, adverse events, ADHD symptoms and comorbidity

The participants will rate emotion regulation with the Cognitive Emotion Regulation Questionnaire (CERQ) pre- and post-intervention. Both participants and parents will (pre- and post-intervention) rate functional impairment in every-day life, ADHD symptoms with total score on the Adult ADHD Self-Report Scale Adolescent version (ASRS-A) and anxiety with total score on the Spence Children's Anxiety Scale (SCAS). Parents will also rate symptoms of oppositional defiant disorder with eight items from the SNAP-IV scale. Post-intervention, participants and their parents will rate adverse events using the Negative Effects Questionnaire (NEQ), and some items targeting client satisfaction (e.g., would recommend the treatment, can better handle emotions and ADHD, has benefitted from the treatment, impressions of the treatment). Difference in ratings between pre- and post-intervention will be calculated using Wilcoxon (paired) signed-rank test. We have no hypotheses in relation to these secondary outcomes, given the small sample size, but expect that these analyses will generate an effect size and enable calculations of appropriate sample size for a future randomized controlled (RCT) study. Post-intervention rating on NEQ and client satisfaction will be presented using descriptive statistics.

Feasibility

The overall aim to assess feasibility will include the outcome measures, as well as information on participants attendance to sessions, completed homework assignments, and the therapist adherence to the intervention measured with self-ratings after each session (rated for different elements of the intervention: “not completed”, “partly completed”, “completed”). We will focus on sample characteristics, data collection procedures and outcome measures, acceptability and suitability of the intervention and study procedures, and preliminary evaluation of participant responses to the intervention.

References

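### Does the loosely worded emotion-dysregulation entry criterion (either informant or both, any or all of four questions) need to be changed?

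*Protocol*

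**What the plan says.** The Participants section plans for nine adolescents with ADHD and emotion dysregulation. The dysregulation criterion is "self- and/or parent-rated emotion regulation difficulties, as indicated by the Emotion Questionnaire, on which the adolescent and parent rate either" of the two disagree categories on one item about changing one's mood. A note adds that "this item encompasses four separate questions related to being i) angry, ii) sad, iii) afraid or iv) happy". The next sentence sets a further condition: "Further, emotion regulation difficulties should be identified as a problem for the adolescent".

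Under Primary outcome measures, "The participants and their parents will rate emotion regulation weekly using the Difficulties in Emotion Regulation Scale Short Form", and in addition "the parents will rate two daily measures of individually defined target behaviors associated with emotion regulation of their child". The hypothesis is that "emotion dysregulation (operationalized as the total summed score of DERS-SF) will decrease" from baseline to intervention. Under Study design, each participant is randomized to a baseline of 5, 6 or 7 weeks. The intervention phase lasts 8 weeks and the post-intervention phase 2 weeks. Analysis is visual (level, trend, variability, immediacy, overlap, consistency), with a Tau-U index as effect size. No DERS-SF score is required for entry.

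**The concern.** One sentence appears to hold two informant rules. Its opening admits an adolescent on the adolescent's rating, the parent's rating, or both. The part that sets the response cut-off joins the two informants with a plain conjunction, which read literally requires both. The four-question item adds a second uncertainty: one qualifying answer might be enough, perhaps the one about being happy, or all four might be needed. Two screeners could therefore enrol different adolescents.

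The possible consequence for analysis concerns the self-rated DERS-SF. If the parent's rating alone suffices, an adolescent who reports no difficulty can enter and still supply a self-rated primary series. If that series starts near its minimum, it cannot show the hypothesised fall, and with nine participants a few such series might colour the conclusion on that outcome.

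**Working it through.** **Do the clauses conflict?** The item is worded in parallel first-person and third-person versions, so two people complete it. On one reading, the and/or phrase is the rule and the later clause says who fills in which version; the clauses then agree. On the other, the later clause is the rule, and the and/or phrase has no function. The first reading gives every word a purpose and is the more natural one. The any-or-all question is not answered in the text.

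**How far could the readings diverge?** The protocol gives no endorsement rates, so every rate here is assumed. Let each informant meet the cut-off in 60% of referrals, with correlation φ between them.

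- P(both) = 0.6 × 0.6 + φ × 0.24 = 0.36 + 0.24φ
- P(either) = 1.2 − P(both)
- Share of either-eligible who fail the both rule = 1 − P(both)/P(either)
- Share entering on the parent's rating alone = (0.6 − P(both))/P(either)

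| φ | P(both) | P(either) | Fail the both rule | Of 9 | Parent only | Of 9 |
|---|---|---|---|---|---|---|
| 0 | 0.360 | 0.840 | 57% | 5.1 | 29% | 2.6 |
| 0.3 | 0.432 | 0.768 | 44% | 3.9 | 22% | 2.0 |
| 0.6 | 0.504 | 0.696 | 28% | 2.5 | 14% | 1.2 |

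The floor argument concerns only the parent-only entrants. Adolescents who qualify on their own rating alone do report difficulty, so the relevant shares are half of the discordant ones. With unequal assumed rates (adolescent 40–60%, parent 60–80%, φ 0.1–0.5), the parent-only share is 27–46%, or about 2.4 to 4.1 of 9. The readings can thus admit different samples.

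**Does parent-only entry imply a floor?** Entry rests on an item about changing one's mood. The DERS-SF is another instrument, and the Hypotheses section lists its subscales as awareness, clarity, nonacceptance, goal-directed behavior, strategies and impulse. No DERS-SF threshold exists on either reading. Requiring both informants would not guarantee room to fall, and parent-only entry does not establish that room is absent.

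**Would a low baseline give a Tau near zero?** Tau-type indices compare baseline points with intervention points by rank. With weekly ratings there are 5 × 8 = 40, 6 × 8 = 48 or 7 × 8 = 56 such pairs per participant. A low series that drops consistently still orders nearly every pair in the hypothesised direction. Only an actual floor, with many ties, or a true lack of change brings the index near zero. The planned inspection of level and variability over 5 to 7 baseline points would show a floor.

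**The case for a change.** The strongest case for acting is that eligibility belongs in the protocol, not in an analysis plan, and that this criterion is stated but not fixed. The any-or-all gap may matter more than the informant rule. If 40% endorsed each question independently (assumed), an any rule would admit 1 − 0.6⁴ = 87% and an all rule 0.4⁴ = 3%; with perfectly correlated answers the gap disappears. The extra condition, that the difficulties be a problem for the adolescent, does not say who judges this, so it narrows parent-only entry without excluding it. The Feasibility section makes sample characteristics a focus, and the secondary analyses look ahead to a randomized trial, so a reproducible entry rule has value. A clarification would cost one sentence.

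What stands is that the sentence is loose and the any-or-all rule is unstated. That bears on how the sample is described, not on whether each participant's comparison of phases is sound. Recording which informant qualified each participant would help description but alter no result. Making the qualifying informant's DERS-SF the primary series would carry its own cost. The primary measure would differ across nine cases, which weakens the planned look at consistency. It would be chosen by the worse screening rating, inviting regression to the mean. It would also be undefined when both informants qualify.

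**Conclusion.** No change to the plan follows. The criterion is ambiguously drafted, and this is a gap that a small team recruiting nine adolescents at one outpatient unit can fill sensibly: either informant suffices, and both complete the item. The plan's analysis does not depend on how it is filled, because every contrast is within a participant against that participant's own 5 to 7 weeks of baseline.

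The divergence between readings could be real: under the equal-rate assumptions 2.5 to 5.1 of 9 places, of which 1.2 to 2.6 are parent-only entries; up to about 4 parent-only under the unequal rates. These figures rest wholly on assumed rates and measure who enters, not bias. A floor on the self-rated DERS-SF is possible under either reading and is established by neither. If one occurred, it would mask an effect in that participant's self-rated series and be visible in the baseline. The parent-rated DERS-SF and the parent-rated daily target behaviors, also primary, would be untouched.

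### No planned quantitative analysis uses the randomised baseline lengths for the timing hypothesis; one supportive randomisation test would do so cheaply

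*Protocol*

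**What the plan says.** The Protocol's title line states that the document includes the analysis plan. Under Study design, nine adolescents enter a single-case multiple baseline study in which "the participants will be randomized to pre-intervention concurrent baselines at different lengths (5, 6 and 7 weeks".

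Under Hypotheses, the Protocol adds that "we hypothesize that time to change will be related to start of intervention, not start of baseline". The same section expects "changes in the DERS-SF subscale scores during the intervention in a manner that corresponds to specific sessions", and that "ratings of the emotional awareness and clarity subscales will change first in the treatment", with three other subscales following. Emotion dysregulation is "operationalized as the total summed score of DERS-SF".

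Under Primary outcome measures, there are weekly ratings ("The participants and their parents will rate emotion regulation weekly using the Difficulties in Emotion Regulation Scale Short Form") and daily ones ("the parents will rate two daily measures of individually defined target behaviors"). The analysis combines visual and quantitative methods. The visual part consists of "investigating level, trend, variability, immediacy of effect, overlap and consistency of data patterns". The quantitative part is Tau-U, described as an effect size, with the index chosen after visual inspection. The only significance test named in the document is the Wilcoxon signed-rank test for secondary pre/post ratings.

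**The concern.** The stated timing hypothesis contrasts two explanations: change that follows each participant's own start of intervention, and change that follows time in the study, for example through repeated rating. Randomising the start points is the design feature that separates them. Of the planned primary tools, only the visual comparison across tiers can use that feature. Tau-U compares each participant's own phases and takes no account of who was assigned which start.

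As planned, a reader therefore cannot say how often the timing judgement would favour the hypothesis by chance. The study is small and exploratory, so no confirmatory claim is at risk. What is lost is a check with a known false-positive rate that the planned data and randomisation already allow.

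**Working it through.** **Inputs from the Protocol.** Nine participants; baselines of 5, 6 or 7 weeks; 8 intervention weeks; weekly DERS-SF; two daily behaviours. The Protocol gives no alpha, power or effect size, so there is no figure to reproduce.

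**Assumptions, not in the documents.** 3/3/3 allocation, SD of one rating = 1, one-sided 5%, autocorrelation AR(1) 0.3 for weekly data, and AR(1) 0.3 or 0.6 per day for daily data.

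**1. Timeline.** Intervention weeks are study weeks 6–13, 7–14 and 8–15 for the three tiers. All tiers are in baseline in weeks 1–5. One tier is in intervention in week 6, two in week 7 and all from week 8. A change at lag L weeks after own start appears in weeks 6+L, 7+L and 8+L, so the stagger carries over to lagged effects.

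**2. Basic Tau by hand.** For an unshifted and a 1-SD-shifted rating with independent normal errors, the expected contribution is 2Φ(1/√2) − 1 = 2 × 0.7602 − 1 = 0.520. Multiply by the fraction of the 8 intervention weeks that is shifted:
- Own start, lag 1: 7/8 in every tier, so 0.520 × 7/8 = 0.46.
- Common step from week 8: 6/8, 7/8 and 8/8, mean 7/8, so 0.46.
- Own start, lag 2: 6/8 in every tier, so 0.39.
- Common step from week 9: 5/8, 6/8 and 7/8, mean 6/8, so 0.39.

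**3. Other indices, simulated (mean over nine cases).**

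| Pattern | Basic | Minus baseline trend | Baseline Theil-Sen slope removed |
|---|---|---|---|
| 1 SD at own start, lag 0 | 0.53 | 0.53 | 0.33 |
| 1 SD at own start, lag 1 | 0.46 | 0.46 | 0.26 |
| 1 SD at own start, lag 2 | 0.39 | 0.39 | 0.21 |
| 1 SD from week 6 for all | 0.45 | 0.40 | 0.02 |
| 1 SD from week 8 for all | 0.46 | 0.46 | 0.27 |
| 1 SD from week 9 for all | 0.39 | 0.39 | 0.21 |
| Drift 0.10 SD/week, no effect | 0.38 | 0.33 | about 0 |

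Slope removal separates drift and the immediate common step, but not the lagged cases. It is also noisier: the SD of the nine-case mean is 0.24, against about 0.13.

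**4. A randomisation test.** Under 3/3/3 there are 9!/(3!3!3!) = 1,680 assignments, with smallest p = 1/1,680 = 0.0006. Randomising within three triads gives 6³ = 216, with smallest p = 0.0046. For each lag L, the statistic is the mean over participants of the sign-aligned difference between ratings before and after own start plus L, over weeks 1–13, divided by that participant's SD. The maximum over L = 0–3, each standardised over the assignments, is referred to its own randomisation distribution.

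| Situation | Rejects, maximum over lags 0–3 |
|---|---|
| No effect, with or without 0.10 SD/week drift (weekly) | 5.0% |
| 1 SD from week 6, 7 or 8 for all (weekly) | 4.4–4.9% |
| 1-SD step at own start, lag 0–3 (weekly) | 30–32% |
| 1-SD step at own start, lag 0–2 (daily, AR 0.3 / 0.6) | 87–88% / 62–64% |
| 1–2 SD ramp over 8 weeks (weekly) | 6–10% |
| Same ramp (daily, AR 0.3 / 0.6) | 8–12% / 7–10% |
| 1 SD arriving in stages (weekly) | 6–9% |
| 1 SD arriving in stages (daily) | 10–13% |

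On weekly data, fixing one lag in advance gives 52–54% for a 1-SD step if the lag is right, 6–8% if it is one week off, and 3–4% if it is two or more off. If lags vary by 0–2 weeks between participants, the maximum version has 16% (1 SD) or 29% (2 SD).

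**5. Several series.** There are four candidates: self- and parent-rated DERS-SF totals and two daily behaviours. Testing each at 5% bounds familywise error at 4 × 5% = 20%. If the series are independent it is 1 − 0.95⁴ = 18.5%.

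**The case against.** A reader might infer that the plan leaves its timing hypothesis unassessed, or that it misuses Tau-U. The documents do not support either reading. Immediacy and consistency across staggered starts are among the planned visual features, and judging a multiple baseline design that way is recognised practice. The Protocol calls Tau-U an effect size and never assigns it the timing question. Even the statement that the hypothesis rests on visual judgement is an inference: the Protocol promises both kinds of analysis and ties neither to this hypothesis.

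Nor does it follow that Tau-U can never help. The matches at 0.46 and 0.39 arise because the common step falls at the mean of the three staggered weeks. A slope-removed index would reveal drift, and the index has not yet been chosen. What stands is narrower: some patterns tied to study time give the same Tau as some tied to own start, and no Tau-U index uses the assignment.

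The strongest objection concerns the remedy. The Protocol expects subscales to change in sequence, so the total may move in stages, where power is close to the 5% null rate. With nine participants, a non-significant result could be misread. This stands as a limit that must be stated. It argues for a supportive role and for a daily series, but not against the test, whose false-positive rate holds in every null situation tried.

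A separate statistical analysis plan could already contain such a test. The Protocol's claim to include the analysis plan weakens that defence without removing it.

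**Conclusion.** The point holds as a cheap improvement, not as an error in the plan. The Protocol randomises start points and states a hypothesis about them, but none of its quantitative analyses uses the assignment. Visual analysis and Tau-U should both stay.

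Under the stated assumptions, a lag-tolerant randomisation test keeps its 5% level under drift and under change tied to baseline start. For an abrupt 1-SD change, power is about 30% on weekly data and about 60–87% on a daily series, depending on autocorrelation. For gradual change of 1–2 SD, or staged change of 1 SD, it is about 6–14%. A larger change arriving in a few distinct blocks would be easier to detect than that range suggests, especially on daily data. The power figures depend on the assumed allocation, SD and autocorrelation; the Tau comparison in step 2 needs only equal tiers and a 1-SD step with independent normal errors.

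**What to change.** Keep the visual analysis and Tau-U as planned, and add one prespecified, supportive between-case randomisation test:

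- State the allocation scheme, and re-draw the 5/6/7-week baselines under that scheme.
- Use the sign-aligned, standardised before/after difference over study weeks 1–13, so that improvement is positive whether a behaviour is meant to fall or rise.
- Either fix the lag in advance from the session content, or take the maximum over lags 0–3 and refer it to its own randomisation distribution. Either choice also gives time to change a working definition.
- Before data are seen, name one main series. One daily target behaviour is preferable because its timing is finer; for each participant, record which of the two behaviours it is. Report the other series descriptively.
- State that power is low for gradual or staged change and falls when lags differ between participants, so a non-significant result is not evidence against an effect.

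The cost is one paragraph and a script that enumerates the assignments. It needs no new data, visits, participants or staff. The price of allowing for lag is lower power for an immediate 1-SD change on weekly data: about 30% instead of about 52%.

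### Does the predicted order of DERS-SF subscale change need a session map and a timing rule fixed in the protocol?

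*Protocol*

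**What the plan says.** The main hypothesis concerns the DERS-SF total and the individually defined target behaviours. The Hypotheses section then adds that subscale scores should move "in a manner that corresponds to specific sessions dealing with content relevant to certain subscales". It gives the order: "We hypothesize that ratings of the emotional awareness and clarity subscales will change first in the treatment, followed by the subscales nonacceptance", together with goals and strategies. Only one subscale is set apart: "An exploratory hypothesis will be adopted for the impulse subscale". A further sentence concerns timing: "Further, we hypothesize that time to change will be related to start of intervention, not start of baseline".

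The Primary outcome measures section plans weekly DERS-SF ratings by adolescent and parent, and visual analysis "investigating level, trend, variability, immediacy of effect, overlap and consistency of data patterns". On the quantitative side it says "To complement the visual analyses, we intend to use Tau-U as an effect size measure".

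The Intervention section describes eight sessions. The content begins with identifying and differentiating emotions and goes on to "tolerance/acceptance of emotions, education of different regulatory skills, as well as on how to select, implement and monitor strategies". No theme is tied to a session number or to a subscale. The Participants section gives as one purpose of the study "to detect mechanisms that could strengthen adaptive regulation skills".

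**The concern.** A directional prediction is made for five subscales, yet the protocol does not say how it will be scored. Three things are open: which session introduces each subscale's content, whether the three later subscales should change together or in turn, and what counts as a first change. The title says that the document includes the analysis plan, so one cannot simply assume that these points are settled elsewhere.

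At stake is the claim about mechanisms. If the session map and the meaning of first change are settled only after the plots have been seen, a favourable order can be read into noisy weekly series. There is a second worry. If immediacy were read only at the start of the intervention, a subscale that changes late, as predicted, would look like a failure.

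**Working it through.** The protocol gives no figure to reproduce, so the check is mainly of the text. The numbers below rest on assumed data and show only what different rules would do.

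**1. What is already fixed.** Setting the two sections side by side (the pairing is a reading, not a statement in the protocol):

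| Content in listed order (Intervention) | Subscale it suggests | Tier (Hypotheses) |
|---|---|---|
| Identifying, differentiating emotions | Awareness, clarity | First |
| Tolerance, acceptance | Nonacceptance | Second |
| Regulatory skills; choosing, applying and monitoring strategies | Strategies | Second |
| No theme named | Goals | Second |

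Two tiers are stated, and the content runs in a compatible sequence. Session numbers, the place of goals and the order within the second tier are missing. A test of early against late subscales needs only the tiers: 2 early × 3 late = 6 pairs per participant and rater.

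**2. Time to change.** Randomised baselines of 5, 6 and 7 weeks address this by design. If change comes in intervention week 2, it falls in study weeks 5 + 2 = 7, 6 + 2 = 8 and 7 + 2 = 9. If it comes in study week 8 whatever the baseline, it falls in intervention weeks 3, 2 and 1. The two patterns can be told apart on the plots, within the precision of weekly ratings.

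**3. Tau.** A basic phase contrast does not carry order. Take baseline 12, 11, 12, 13, 12 and intervention 9, 9, 9, 9, 12, 12, 12, 12. There are 5 × 8 = 40 pairs. The four 9s give 4 × 5 = 20 improvements. Each 12 gives one improvement, one worsening and three ties, a net of 0. Tau = 20/40 = 0.50, and reversing the intervention values also gives 0.50. But the protocol assigns Tau-U to effect size, not to order.

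**4. Immediacy.** Assume three-week windows and a 2-SD step at session 5. At intervention start the difference is 0.0 SD. At session 5 it is 2.0 SD, and one week off it is 2 × 2/3 = 1.33 SD. The penalty on a late subscale arises only if immediacy is read solely at intervention start, which the protocol does not say.

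**5. Would a formal rule do better?** One candidate takes the best-fitting step in intervention weeks 1 to 8, counted if it is at least 0.75 pooled baseline SD. A pair supports the order if both subscales changed and the early one came first. It opposes the order if the late one came first or only the late one changed. Otherwise it is neutral. The simulation used 3,000 runs and nine cases, giving 9 × 6 = 54 pairs. It assumed early change at session 2, late change at session 5, AR(1) 0.3 and noise correlation 0.5.

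| Truth | Support/oppose, 1 SD | Support/oppose, 2 SD |
|---|---|---|
| Order true | 40% / 24% | 82% / 7% |
| All improve gradually together | 22% / 34% | 32% / 34% |
| Only early subscales change | 16% / 9% | 21% / 5% |
| Only late subscales change | 11% / 60% | 14% / 78% |
| No change at all | 6% / 21% | same |

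About a third of series are called changed when nothing has changed. In that case early and late series are alike, so either comes first equally often (6%). The remaining 21 − 6 = 15 points are pairs in which only the late one crossed the threshold. The mirror-image pairs count as neutral, so the rule tilts against the hypothesis. At 1 SD the 5th to 95th percentile ranges of support overlap: 22% to 59% if the order is true, 9% to 37% under common gradual improvement.

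**The case for a change.** The strongest case for a change is that the sessions on which the prediction depends are part of the hypothesis itself, are known to the developers, and would cost one table to write down. The definition also matters. Three plausible first-change rules were compared on simulated pairs (6 baseline and 8 intervention points, SD 1.5, drop of 3 points, independent errors; all assumed). With true onsets at weeks 2 and 5 they disagreed on the order in 51% of pairs, and the correct order was found in 60% to 82% depending on the rule. With equal onsets they disagreed in 70%.

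This stands as a description. The protocol leaves room for judgement, and a reader of the results should know it. But the same figures show how little eight weekly points say about order under any one rule. Fixing a rule in advance removes the choice between rules; it does not make a single case's order reliable. The planned reading of level, trend and consistency of patterns across nine participants and two raters is a reasonable way to look for an order. Nor does the protocol promise a test or an error rate for it.

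**Conclusion.** The text does leave open the session numbers, the order within the second tier and the meaning of first change. No rule that it states gives a wrong result. The developers can supply the session content from the intervention itself, and analysts experienced with single-case data would read the weekly subscale plots against it. The scoring rule examined is a trade-off, not a clear gain: it separates well at 2 SD, poorly at 1 SD, and leans against the hypothesis when nothing changes.

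The point is minor. It concerns one supporting hypothesis in a feasibility study of nine, whose order result can only be descriptive. The contrasts for the DERS-SF total and the target behaviours do not depend on it. The textual conclusion rests on the protocol alone. The percentages rest on assumed effect sizes, session timing and correlations, and illustrate rather than predict.
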